13.2 Adverse Events

All AE summaries will be restricted to TEAEs, which are defined as those AEs that occurred after dosing and those pre-existing AEs (prior to first application of study treatment) that worsened during the study. If it cannot be determined whether the AE is treatment emergent due to a partial onset date, then it will be counted as such. Verbatim terms in the eCRFs will be mapped to SOCs and PTs using MedDRA (Version 24.0). The one exception will be the summary of Any AE which will include AEs not considered treatment-emergent. The summary of Any AEs will be reported in the Overall Summary of Adverse Events.

For subjects not rolling over to the OL-LTE study, all reported AEs will be included in the Double-Blind phase summaries. For subjects rolling over to the OL-LTE study, all AEs with an onset date on or before the Week 8 visit date will be included in the Double-Blind phase summaries.

Imputation of start and end dates of AEs

To calculate duration of AEs, the following rules will be used where applicable to impute partial or completely missing start dates or end dates:

• If only the day is missing for a start date, the 1st of the month will be imputed. If the new estimated date falls before the date of first dose, while the known month and year match the month and year of the first dose, the date of first dose will be used as the new estimated date. The AE will be considered as a treatment-emergent AE (TEAE).

- If only the day is missing for an end date, the last day of the month will be imputed. If the new estimated date falls after the date of last study visit, the date of last study visit will be used as the new estimated date. Last study visit is defined as the Week 8 visit for those who elect to participate in the OL-LTE study, or the Week 9 follow-up visit for those who fail to qualify for participation in the OL-LTE study, or who qualify to participate but ultimately elect not to enroll.
- If both the day and the month are missing for a start date or end date, no imputation will be used, and the duration will not be calculated. However, if the year of start is the same or greater than the year of the first dose date, the AE will be considered as a TEAE.
- If the start date or end date is completely missing, duration will not be calculated. However, an event with completely missing start date will be considered as a TEAE.

Imputation of missing relationship and/or missing severity

If relationship to treatment is missing, the event will be conservatively treated as related to study drug.

If severity is missing and the AE is reported as serious and fatal, severity will be imputed as CTCAE=5. If severity is missing and the AE is reported as serious and not fatal, severity will be imputed as CTCAE=4. If severity is missing and the AE is not reported as serious, severity will be imputed as CTCAE=3.

All AEs will be listed by treatment and by subject, detailing the verbatim term given by the investigator, the SOC, PT, onset date and time, end date and time, duration (days), common terminology criteria for adverse events (CTCAE) grade, outcome, relationship to study drug, action taken with study drug, other action taken to treat the event, seriousness, and criteria for seriousness. Serious AEs (SAEs), TEAEs leading to study discontinuation, and TEAEs related to study drug will also be listed separately. The following adverse events of special interest (AESIs) will be identified and listed separately: contact dermatitis, follicular event, and headache.

All AEs will be summarized by treatment as incidence rates of:

• Any AE

TEAEs will be summarized by treatment as incidence rates of:

- Any TEAE
- Any AESIs
- Any treatment-related TEAE
- Any TEAE leading to study drug discontinuation
- Any TEAE leading to study discontinuation
- Any SAE (non-Fatal)

- Any serious TEAE
- Death
- Treatment-related Serious TEAE
- Serious TEAE leading to study drug discontinuation
- Serious TEAE leading to study discontinuation
- TEAE (COVID-19) (i.e., positive COVID-19 diagnosis)

Individual PTs will be summarized by treatment according to the following:

- All TEAEs by SOC and PT in descending order of frequency for Tapinarof Cream 1% (also for treatment-related TEAEs, TEAEs leading to study drug discontinuation, TEAEs leading to study discontinuation and serious TEAEs)
- All TEAEs by SOC, PT, and maximum CTCAE grade
- All TEAEs by SOC, PT, and maximum causality (not related, related) to the study drug

In addition, TEAEs and serious TEAEs will be summarized by SOC (alphabetical order) and PT (descending order) for the following subgroups:

- Age (2-6 yrs, 7-11 yrs, 12-17 years, \geq 18 years)
- Sex
- Race (White, Asian, Black or African American and Other)

At each level of summarization, a subject will be counted once if he/she reported one or more events. The severity of TEAEs and relationship to study drug will be summarized in a similar manner. For summaries of relationship to study drug, a subject will be classified according related or not related. For summaries of TEAE CTCAE grade, a subject will be classified according to the worst grade.

For treatment-emergent AESIs, summarization will be more extensive, reflecting the more detailed information collected. Information summarized will include number of events per subject, earliest onset day, duration (in days), causality, grade, and seriousness of AESIs, outcome, actions taken with study drug, assorted physical characteristics of the AESIs, and demographic/baseline characteristics and vIGA-ADTM status. Each type of AESI will be summarized separately. If a subject has more than one treatment-emergent occurrence of an AESI, the subject's maximum duration, highest levels of causality and seriousness, maximum grade and generally the most extreme level of each characteristic will be summarized. If an AESI is ongoing at time of study completion/discontinuation, it will not be included in the duration summary.

A Kaplan-Meier figure will be generated for each treatment-emergent AESI of time to first event. Subjects not experiencing the AESI will be censored at the date of study completion or discontinuation.

For purposes of CT.gov reporting, two additional summaries of AEs by SOC, PT and treatment group will be done as follows:

- including only PTs >= 1% (in either treatment group)
- including only PTs \geq 5% (in either treatment group)

Each of these two summaries will include a total row summarizing the number of subjects with at least one of the PTs that meet the corresponding threshold.

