Study drug application under supervision ^v		X	X	X		X				
Enrollment (optional) in OL-LTE study								X		

a. The Follow-up Visit will be performed for any subject who completes Visit 6/Week 8 but fails to qualify for participation in the OL-LTE study or qualifies to participate in the OL-LTE study but elects not to enroll in that study. A follow-up visit is not required for a subject who early terminates.

b. Subjects who withdraw from the study before Visit 6 (Week 8) will complete an Early Termination Visit. A follow-up visit is not required for a subject who early terminates.

c. Phone calls to assess AEs and concomitant medications, to review study drug application procedures, and to confirm subject's continued participation in the study. Subjects should be reminded to complete the diary and bring it with them to the next clinic visit.

d. Medical history will include year of AD diagnosis, CV family history, allergic conditions, and risk factors (including height, weight, medical conditions) and family history of liver disease. As part of the subject's medical history, all systemic (oral and injectable) medications used by the subject for treatment of AD prior to 30 days before the Screening visit will be collected.

e. Review medical history at Baseline and record any changes.

f. Serum pregnancy test to be performed at the Screening visit only and urine pregnancy test to be performed at subsequent clinic visits when pregnancy testing is performed.

g. Urine pregnancy test to be performed before randomization.

h. Physical examination will include height and weight (BMI will be calculated in the CRF) at the Screening visit; a brief physical examination will be performed at other visits.

i. Vital signs will include blood pressure, pulse rate, and body temperature and should be measured after the subject is seated for at least 5 minutes. Vital signs will be measured before blood collection for clinical laboratory assessments and PK analysis (where applicable).

j. ECGs will be collected in a subset of subjects and will be collected prior to study drug administration in clinic. Informed consent/assent will be required.

k. Includes serum chemistry and liver chemistry tests, and hematology.

l. Blood sample collection for clinical laboratory tests is not required at the Baseline Visit if it has been ≤14 days since samples were collected at Screening and the results of those clinical laboratory tests were not clinically significant.

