Study drug application instructions will be reviewed at all post-randomization clinic visits and during any planned study phone calls. On clinic visit days, subjects and/or caregivers will be instructed/reminded on how to apply study drug (except during the final treatment/end-of-study visits). During the clinic visits, subjects or their caregivers will apply the daily dose of study drug while on-site under the supervision of site personnel after efficacy and safety assessments have been completed, with the exception of the local tolerability scale (LTS) at some visits (as outlined in the Schedule of Assessments [Protocol Table 1]). The time of the dose application and assessments will depend on the time of the clinic visit. Therefore, the timing of the clinic visit may lead to a change in the subject's chosen dosing time for that day.

At the end of the 8 weeks of assessments in this study, subjects will have the option to enroll in an Open-Label, Long-Term Extension (OL-LTE) study for an additional 48 weeks. Subjects who complete Visit 6/Week 8 but choose not to participate in the OL-LTE study or who fail to qualify for participation in the OL-LTE study will complete a Follow-up Visit (Visit 7/Week 9 visit) approximately 1 week after the end of treatment in this study. Subjects who withdraw from the study before Visit 6/Week 8 will complete an Early Termination Visit as their final visit and are not eligible for the OL-LTE study. The subjects who complete the Early Termination Visit must not complete a Follow-Up Visit.

Study duration for subjects who complete this Phase 3 study and who fail to qualify for participation in the OL-LTE study, or who qualify to participate in the OL-LTE study but elect not to enroll in that study is approximately 13 weeks in total. Study duration for subjects who complete this Phase 3 study and are eligible and decide to participate in the OL-LTE study is approximately 12 weeks in total.

Efficacy assessments will include the validated Investigator Global Assessment for Atopic Dermatitis (vIGA-ADTM) score, percentage of total body surface area (%BSA) affected, Eczema Area and Severity Index (EASI), PP-NRS,

Safety assessments will include

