7. NOTATION OF TREATMENT GROUPS AND VISITS

Notation of treatment groups

The following notation of **treatment groups** will be used throughout the report:

Full Notation (as used in the study protocol)	Notation Used Throughout All Tables, Listings, and Figures
Tapinarof Cream 1%	Tapinarof Cream 1%
Vehicle	Vehicle Cream

Visit terminology

Visit	Notation Used Throughout All Tables, Listings, and Figures
Screening, Days -30 through Day -1, Visit V1	Screening
Baseline, Day 1, Visit V2	Baseline
Week 1, Day 8, Visit V3	Week 1
Week 2, Day 15, Visit V4	Week 2
Week 4, Day 29, Visit V5	Week 4
Week 8, Day 57, Visit V6 (End of Treatment)	Week 8
Week 9, Day 64, Visit V7 (End of Study/Follow-up) [1]	Week 9

Note: phone calls to assess AEs and concomitant medications, to review study drug application procedures, and to confirm subject's continued participation in the study will occur on Week 3 (Day 22) and Week 6 (Day 43).

[1] Subjects who choose not to participate in the OL-LTE study or who fail to qualify for participation in the OL-LTE study will complete a Follow-up Visit (Week 9 visit) approximately 1 week after the end of treatment in this study.

Analysis visits

Study days are measured from date of first dose of study medication. Study days corresponding to measurements are calculated as:

- Assessment date date of first dose + 1 if assessment date is on or after the date of first exposure of treatment.
- Assessment date date of first dose if assessment date is before the date of first exposure of treatment.

All efficacy and safety endpoints will be analyzed according to the nominal visits (i.e., actual visit) except for assessments collected on early termination and unscheduled visits. Early termination and unscheduled visits will be re-numbered to an analysis visit based on their windowed visits defined by actual study day. If more than one visit occurs within a single visit window, then the analysis will take the one closest to the target day. If the 2 visits are equidistant from the target day, the visit with later date and time will be used.

The following analysis visit windows will apply to early termination and unscheduled visits:

Analysis Visit	Target Day	Analysis Visit Window
Baseline	1	1
Week 1	8	Post first dose to Day 12
Week 2	15	Day 13 – Day 21
Week 4	29	Day 22 – Day 42
Week 8	57	Day 43 – Maximum (last day of treatment + 3 days, Day 59)
Week 9	64	>Maximum (last day of treatment + 3 days, Day 59)

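### The double-blind AE window ends at Week 8 for subjects who enter the extension and at Week 9 for completers who do not, and its date-based cut-off does not exclude events after a same-day open-label dose

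*SAP*

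**What the plan says.** SAP Section 13.2 gives two rules. For subjects who do not enter the extension: "For subjects not rolling over to the OL-LTE study, all reported AEs will be included in the Double-Blind phase summaries". For those who do: "all AEs with an onset date on or before the Week 8 visit date will be included in the Double-Blind phase summaries". The same section sets the final visit to match: "Last study visit is defined as the Week 8 visit for those who elect to participate in the OL-LTE study", and Week 9 for completers who do not enroll. SAP Section 7 puts Week 8 at Day 57 (end of treatment) and Week 9 at Day 64. This agrees with Protocol Section 10.4.3, which runs AE summaries from first dose to the final study visit.

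The TEAE definition in SAP 13.2 has no upper time limit. TEAEs and AESIs are summarized as incidence by treatment, and no exposure-adjusted rate is planned. The AESI Kaplan-Meier figures censor at study completion or discontinuation. No formal safety comparison is made (SAP Section 13).

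In Protocol Table 1 the row "Enrollment (optional) in OL-LTE study" is marked at the Week 8 visit, and Protocol Section 7.6 lists the same step. No double-blind drug is applied at that visit (Table 1, footnote r). Protocol Section 3.3 leaves the details of the extension to a separate protocol. The AE listing in SAP 13.2 includes "onset date and time", but the cut-off rule uses only the date.

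**The concern.** Entering the extension happens after randomization. It depends on the subject's choice and on having taken at least 80% of intended doses (Protocol Section 3.3). The trial itself plans on different response (45% against 25%) and different loss (15% against 30%) by arm, so equal shares of non-rollover completers cannot be presumed. If the shares differ, one arm's crude incidence includes more off-drug person-time than the other's. Elsewhere the plan keeps that week apart: Week 9 is a separate analysis visit for efficacy (SAP Section 7), and post-baseline local tolerability is scored only within 48 hours of an application (Protocol Section 6.3.6).

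The second issue is the Week 8 day itself. A calendar-date cut-off cannot separate events before a first open-label dose from events after one on the same day. If a former vehicle subject received open-label tapinarof that day and had contact dermatitis or a headache, both AESIs, the rule would place the event under vehicle.

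**Working it through.** **1. The plan's own figures.** Screening is 30 days, treatment 8 weeks = 56 days, follow-up 64 − 57 = 7 days.

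- Not rolling over: (30 + 56 + 7)/7 = 13.29 weeks. The SAP says such a subject who may "elect not to enroll in that study is approximately 13 weeks in total".
- Rolling over: (30 + 56)/7 = 12.29 weeks, against a stated figure of about 12.

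Both stated durations are reproduced to rounding.

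**2. Window for completers.** Day 64 against Day 57: 7 extra days, 7/57 = 12.3%, all off treatment. Early terminators also do not roll over, but they have no follow-up visit and gain nothing from the rule.

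**3. Added incidence per non-rollover completer.** Assume incidence p by Day 57 and a constant hazard: λ = −ln(1 − p)/57, added first-event probability = (1 − p)(1 − exp(−7λ)).

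- p = 0.30 (assumed): 3.00 points.
- p = 0.50 (assumed): 4.08 points.

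**4. From subject to arm.** Let d be loss by Week 8 (SAP Section 5: 15% tapinarof, 30% vehicle) and r the rollover share among completers (not in the documents, so assumed). Non-rollover completers as a share of those randomized: s = (1 − d)(1 − r). Extra days from the rule = 7s. Shift in crude incidence = difference in s × the value from step 3. All differences are tapinarof minus vehicle.

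| r tapinarof / vehicle | s tapinarof / vehicle | Difference in s (points) | Extra days | Shift, p = 0.30 | Shift, p = 0.50 |
|---|---|---|---|---|---|
| 90% / 90% | 8.5% / 7.0% | +1.5 | +0.1 | under 0.1 | +0.1 |
| 50% / 50% | 42.5% / 35.0% | +7.5 | +0.5 | +0.2 | +0.3 |
| 95% / 80% | 4.25% / 14.0% | −9.75 | −0.7 | −0.3 | −0.4 |
| 90% / 60% | 8.5% / 28.0% | −19.5 | −1.4 | −0.6 | −0.8 |
| 60% / 90% | 34.0% / 7.0% | +27.0 | +1.9 | +0.8 | +1.1 |

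The sign changes with the assumed rollover shares, and the largest shift in the table is 1.1 points.

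**5. Scale.**

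- The sampling standard error of an incidence difference is √[p(1 − p)(1/267 + 1/133)] = 4.9 points at p = 0.30 and 5.3 points at p = 0.50.
- Unequal early loss shortens mean vehicle follow-up by (0.30 − 0.15) × (57 − t) days, where t is the mean dropout day (assumed): 2.1 days at t = 43, 4.2 at t = 29, 6.3 at t = 15. This exceeds every entry in the days column.

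**6. Week 8 day.** It is 1 of 57 days (1.8%), an upper bound on the time that could include an open-label dose. The number of misplaced events depends on whether open-label drug is applied that day and on the first-day reaction rate. The documents give neither, so no figure is derived.

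**The case against.** A reader might infer that the arms are compared over unequal time. The documents do not support that as a general statement. The rule divides subjects by rollover status, not by arm, and no rollover rates are given. An excess of non-rollover completers on vehicle would partly offset the larger follow-up deficit from vehicle dropout.

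A reader might also infer that the double-blind tables are contaminated by open-label drug. That needs a first open-label dose on the Week 8 date, which no passage states. Events that day before any such dose are genuine double-blind events, and the listed onset time would allow the rest to be identified.

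Other points also stand:

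- Signs of the disease under study are not AEs unless more severe than expected (Protocol Section 8.1.1), so post-treatment flares would largely stay out.
- A constant hazard applies the on-drug rate to an off-drug week.
- Safety is descriptive, and Kaplan-Meier censoring already accommodates different follow-up lengths.
- The windows follow Protocol Section 10.4.3. Replacing the main tables with a Week 8 cut-off would depart from it, while SAP Section 14 declares no changes.

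These points limit the size of the issue and argue against replacing the main tables. They do not remove the two gaps: the window follows a post-randomization status with no common-window summary beside it, and the date rule ignores the onset time that the listing contains.

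**Conclusion.** The point holds in a limited form and is minor. The window is 7 days longer for completers who do not roll over than for subjects who do. Crude incidence by arm moves only if the share of non-rollover completers differs by arm. The direction is unknown, and the effect is about 1 point or less. That size rests on assumed incidences of 30% to 50%, assumed rollover shares, a constant hazard and the SAP's planned loss. A between-arm bias is not shown.

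Misplaced events on the Week 8 day are possible under the rule as worded, but only if open-label tapinarof is first applied that day. Contamination is therefore a gap in the rule, not a finding.

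**What to change.** In SAP Section 13.2:

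1. For rollover subjects, count an AE in the double-blind summaries only if its onset precedes the first OL-LTE dose, in addition to the present Week 8 date limit. Use onset time for events on the day of that dose, and state how an event with no onset time is classified.
2. Keep the main summaries to the final study visit, as Protocol Section 10.4.3 requires.
3. Add a supplementary TEAE and AESI summary with one cut-off for all subjects: onset up to the Week 8 or Early Termination visit and before any OL-LTE dose. Show Week 8 to Week 9 events separately.
4. Leave the Kaplan-Meier censoring as it is, apart from excluding events after the first open-label dose.

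The cost is SAP wording and one or two tables. AE onset time is already listed; the date and time of the first extension dose would have to be brought in from the extension study. The change does not remove the imbalance from unequal early dropout, and a footnote to the supplementary table should say so.

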8.3 Time Period and Frequency for Event Assessment and Follow-Up

8.3.1 Adverse Event Reporting

All AEs will be collected from the time of signed informed consent until the final visit.

Any AEs assessed as related to study participation (e.g., protocol-mandated procedures, invasive tests, or change in existing therapy) will be collected from the time a subject consented to participate in the study up to and including any follow-up contact.

All SAEs will be recorded in the CRF and reported to the Sponsor within 24 hours via email or phone (refer to [Medical Monitor / Sponsor Information Page](#) for contact information) (see Section 8.4).

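### The missing-start-day rule in SAP 13.2 ignores the end date, so read literally an AE that resolved before first dose becomes a Day 1 TEAE with zero or negative duration

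*SAP*

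**What the plan says.** SAP 13.2 defines TEAEs as "those AEs that occurred after dosing and those pre-existing AEs (prior to first application of study treatment) that worsened during the study". It then sets a default for uncertain cases: "If it cannot be determined whether the AE is treatment emergent due to a partial onset date, then it will be counted as such".

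The date rules follow under a separate sub-heading, introduced as "To calculate duration of AEs, the following rules will be used where applicable to impute partial or completely missing start dates or end dates". Three of them concern the start date:

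- **Day missing.** "If only the day is missing for a start date, the 1st of the month will be imputed". If that date is before first dose and the recorded month and year are those of first dose, the start is moved: "the date of first dose will be used as the new estimated date. The AE will be considered as a treatment-emergent AE (TEAE".
- **Day and month missing.** No date is imputed and no duration is calculated. The AE is a TEAE if the start year is the first-dose year or later.
- **Start completely missing.** No duration is calculated, and "an event with completely missing start date will be considered as a TEAE".

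None of the three refers to the end date. Protocol 8.3.1 fixes the collection window: "All AEs will be collected from the time of signed informed consent until the final visit". SAP section 7 places screening at Days -30 through -1.

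**The concern.** A complete end date before first dose settles the question of treatment emergence, whatever is missing from the start date. The event did not occur after dosing and cannot have worsened after dosing. The missing-day rule nevertheless labels it a TEAE and gives it an onset later than its own end.

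Such a record would be counted in the TEAE tables. If the term is headache, contact dermatitis or a follicular event, the effect goes further. SAP 13.2 summarizes earliest onset day and duration for AESIs and draws a Kaplan-Meier figure of time to first event. The record would enter as a Day 1 onset, possibly in place of a later genuine first event, and could put a zero or negative value in the duration summary.

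The SAP already uses end dates in the parallel situation: section 9.5 separates prior from concomitant medications by their stop dates. The AE section has no equivalent check.

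**Working it through.** The plan states no figure here to reproduce. The check applies the rule as written to single records.

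**Inputs**

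- Start rule for a missing day: SAP 13.2, as above.
- Duration = date2 - date1 + 1, where date2 is described as the later date: SAP Appendix A, Standard Calculations.
- Study day = assessment date - first-dose date + 1, on or after first dose: SAP section 7.
- Illustrative dates (assumed): first dose 20 March; start recorded as March, day missing.

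**Step 1: imputed start.** The 1st of March is before 20 March and the month and year match, so the start becomes 20 March. Study day = 20 - 20 + 1 = 1. TEAE = yes, whatever the end date.

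**Step 2: duration by recorded end date**

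| End date | Duration (days) | TEAE under the rule | Status shown by the end date |
|---|---|---|---|
| 5 March | 5 - 20 + 1 = -14 | yes | ended before dosing |
| 10 March | 10 - 20 + 1 = -9 | yes | ended before dosing |
| 18 March | 18 - 20 + 1 = -1 | yes | ended before dosing |
| 19 March | 19 - 20 + 1 = 0 | yes | ended before dosing |
| 25 March | 25 - 20 + 1 = 6 | yes | cannot be determined |
| March, day missing (imputed 31 March) | 31 - 20 + 1 = 12 | yes | cannot be determined |

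The first four rows are wrong. The last two are what the default is meant for.

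**Step 3: is the example special?** Take every pair of first-dose day and earlier end day within one 31-day month: 31 × 30 / 2 = 465 pairs. Of these, 30 have the end exactly one day before dosing (duration 0). The other 465 - 30 = 435 give a negative duration, down to -29. No pair gives a valid duration. These are counts of possible dates, not expected event frequencies.

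**Step 4: the other two start-date rules.** Neither imputes a date or calculates a duration. An AE with only the year recorded, or no start date at all, and a recorded end before first dose is still called a TEAE, but the rule gives it no Day 1 onset and no negative duration.

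**Step 5: how often could the missing-day rule apply?** The start must fall in the calendar month of first dose. Assume a full 30-day screening period, start days spread evenly, first-dose dates spread evenly over 2022, and an event that ends before dosing. The share of such events starting in the first-dose month is then:

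| Event length | Share |
|---|---|
| 1 day | 49% |
| 6 days | 41% |
| 11 days | 33% |
| 15 days | 26% |

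A start in the previous month is neither moved nor flagged. These shares apply only to resolved screening AEs whose start day is missing, and the documents do not say how many there will be.

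**The case against.** The strongest reply is that SAP 13.2 already contains the right principle. The definition and the default for undeterminable cases come first. The date rules are introduced for calculating duration and apply where applicable. A programmer could exclude an AE with a recorded end before dosing without any change to the text. This stands in part: a reader might infer that the date rules override the definition and that every affected record will be wrong, and the documents do not say so. What remains is that the missing-day rule itself assigns TEAE status without condition, and nothing reconciles it with the definition. SAP Appendix B has derived datasets programmed twice, and two programmers could read the section differently.

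There are also safeguards. Protocol 8.1.3 has sites collect duration and time to onset for AESIs, Protocol section 9 provides for querying inconsistencies, and an end before a start falls outside the Appendix A formula, so it may be noticed. Where a subject has more than one occurrence of an AESI, the maximum duration is summarized, which can hide a negative value. These lower the chance of a visible error but do not correct the TEAE flag.

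Over-counting TEAEs is conservative, and screening events precede randomization, so neither arm is favoured. That supports the default when status is unknown. It does not support it when the end date answers the question, and a negative duration is not conservative.

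**Conclusion.** The point holds as a small defect in a stated rule. Read literally, the missing-day rule turns an AE with a recorded end before first dose into a Day 1 TEAE, with duration 0 if it ended the day before and negative if it ended earlier. This conflicts with the TEAE definition and the default in the same section. The year-only and fully missing start rules share only the misclassification.

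Two stronger readings are not supported. One is that all three start-date rules produce negative durations; only the missing-day rule imputes a start date. The other is that about half or more of resolved screening AEs with a missing start day would be affected. The 49% is a share of all screening days and holds only for one-day events over a 30-day screening period. Shorter screening periods would raise the share of days (75% for 14 days, 87% for 7 days), but the documents give only the Day -30 to Day -1 window.

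The number of affected records is not given and is probably small. SAP section 13 plans no formal safety comparison, and no efficacy result is touched. The result rests on a literal reading of the rule and, for the duration error, on a complete recorded end date.

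**What to change.** Make two changes in SAP 13.2.

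1. State once, for all three start-date rules, that an AE whose recorded end date is before first dose is not treatment-emergent. If the end date is partial, apply the test to its latest possible date.
2. In the missing-day rule, move the start to the first-dose date only if the end date is on or after first dose, missing, or too incomplete to place before first dose. Otherwise impute the later of the 1st of the month and the consent date, capped at the end date.

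This gives a single imputed date in every missing-day case. For first dose 20 March and consent on or before 1 March (assumed):

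- End 10 March: start 1 March, not a TEAE, duration 10 - 1 + 1 = 10 days.
- End 19 March: start 1 March, not a TEAE, duration 19 - 1 + 1 = 19 days.
- End 25 March: still a TEAE, start 20 March, duration 6 days.
- End date missing: still a TEAE, start 20 March.

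No truly ambiguous event loses its TEAE status. The cost is a short addition to the SAP and a small change to the AE derivation, with no new data collection.
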